### 5.3.1 Substitution of subjects

The sponsor, with prior authorization from the research ethics committees, may decide to replace subjects who withdraw their FCI or those who are lost to follow-up, if it is necessary to balance the study groups so that they are evaluable, or to complete the minimum population to be evaluated for the efficacy analysis.

The results obtained from the replaced subjects will continue to be used for safety analysis.

## 5.3 Lifestyle considerations

For the study, participants may need to modify some lifestyle activities to accomplish the following:

- Refrain from smoking.
- Refrain from using electronic vaporizers.
- Avoid immersing yourself in water without eye protection ( *goggles* ).
- Avoid direct exposure to fans (including air conditioning vents) during activities that involve vision. 24 hours before your checkup visits.
- Maintain your sleep-wake cycle with the one you entered the study.

## 5.4 Scrutiny failures

A screening failure is defined as a participant who agrees to participate in the study, giving their consent, but who is not assigned to a treatment group; that is, they do not enter the study. The following information regarding screening failures must be reported, at a minimum:

- Demographic data.
- Details of the counting failure (specify whether due to eligibility criteria, which one, or some other reason for the failure).
- Presence of serious adverse events during the scrutiny.

This is necessary to comply with the CONSORT ( *Consolidated Standards of Reporting Trials* ) guidelines for publishing results or to respond to potential questions from regulatory authorities.

Subjects who do not meet the eligibility criteria for participation in the study due to a specific modifiable factor may be re-screened. Subjects in this situation must use the same initial screening number.

## 5.5 Recruitment and retention strategies

This is a Phase I-II study planned for six centers. The selected centers will be responsible for subject recruitment. Recruitment will be competitive, with a proposed initial recruitment of 21 subjects per center; however, this will be contingent on the performance of each center, so this number may vary by center.

The minimum expected recruitment rate per center is 0.2 subjects per day.

Subject participation in the study is approximately 35 days, during which time they are only required to attend two visits after the baseline visit, so retention issues are not anticipated. However, subjects will be eligible for travel and travel expenses to attend their visits. Other strategies to improve subject retention include, but are not limited to:

- Clearly communicate the importance of the study and the benefits the population will gain from its results.
- Make calls or send text messages to remind yourself of appointments or activities to do.
- Provide a printed calendar and ID card to remind you of upcoming appointments and activities, as well as their estimated duration.
- Offer flexible business hours.
- Systematic organization of the study procedures, so that the subject does not stay longer than necessary during his visit.
- Minimize subject wait times.

All materials to be delivered to the subject or recruitment strategies implemented by the Centers will be submitted for approval by the corresponding committees.

## 5.6 Procedure in case of loss of follow-up

For this protocol, loss to follow-up is defined as those subjects who were randomized, who at some point were active subjects in the study, but their final evaluation could not be completed.

If the participating subject does not attend their appointment, the research site will call to determine the reason and attempt to schedule a new appointment within the established window or an unscheduled appointment. If an appointment cannot be scheduled, the subject will be asked about the presence of adverse events and the reason for discontinuing the study, as minimum information.

A loss to follow-up <5% is not considered to represent a problem for the validity of the results obtained. [26, 27]

## 5.7 Subject identification

Study subjects will be identified by a number and the initials of their name.

[figure not shown]
The initials of the subject of study will be obtained starting with the first letter of the name, followed by the first letter of the first surname and the first letter of the second surname, obtaining a maximum of three letters. In case the person has two names or a compound surname, the first letter will always be used.

### Example:

During the screening phase, participants will be assigned a consecutive three-digit number. Once the subject has been selected, they will be assigned a number that will identify them throughout the study. This code will consist of eight numbers in the following order, from left to right:

- three digits of the molecule under study according to the name given by the sponsor.
- two digits corresponding to the research center number.
- three digits of the consecutive number assigned to its inclusion in the research center.

### Example:

## 6. Investigational product

---

### 6.1 Managed Products

#### 6.1.1 Investigational product

- Generic name: Propylene glycol
- Distinguishing name: Nanodrop® (PRO-176)
- Active ingredients: Propylene glycol 0.6%.
- Pharmaceutical form: Ophthalmic emulsion
- Presentation: multi-dose dropper bottle, 10 ml.
- Prepared by: Laboratorios Sophia, SA de CV
- Solution description: Homogeneous emulsion, free of visible particles.
- Packaging description: White bottle with a capacity of 10 mL, made of low-density polyethylene.

#### 6.1.2 Reference product

- Generic name: Propylene glycol
- Distinguishing name: Systane® Balance
- Active ingredients: Propylene glycol 0.6%
- Pharmaceutical form: Ophthalmic emulsion
- Presentation: multi-dose dropper bottle, 10 ml.
- Manufactured by: Alcon Laboratories, Inc.

##### *6.1.2.1 Justification of the reference product*

Systane® Balance is a commercially available lubricant with a previously described safety and efficacy profile. It is a propylene glycol ophthalmic emulsion at the same concentration as Nanodrop®. Furthermore, it will be a direct commercial competitor.

#### 6.1.3 Dosage of investigational products

The minimum dosage to follow is 1 drop, four times a day, in both eyes.

However, subjects may increase the number of applications, if they deem necessary, as many times per day as they deem necessary. Each application must be recorded in the "Subject Diary."

##### *6.1.3.1 Justification of the dose*

Ophthalmic lubricants are generally prescribed as needed (pro re nata [PRN]). [28] However, the study by Asbell et al. compared the efficacy of QID versus PRN dosing. Their results showed that, although there was no difference in clinical signs, the QID group had greater symptom improvement. [29] For this reason, the minimum dosage proposed for this study, and as the basis for calculating adherence, is 1 drop four times daily. However, the possibility of increasing this PRN dosage remains open to assess whether more applications are better for the patient.

## 6.2 Storage and handling of research products at the study center

Delivery will be made via a courier service contracted by the sponsor, specifically selected for this purpose, to the address of the research center in accordance with the study plan.

Reception will be carried out by the assigned research team staff. They must verify the condition of the primary packaging (box). If it shows alterations or defects in its integrity that, in their judgment, could have damaged the contents, they must report this to the sponsor. If the package shows no significant defects, they will proceed to open it.

Inside, you should locate the receipt acknowledgment document and the temperature *data logger* . You should check that the recorded temperature meets the specifications for its transport and storage. You will verify the contents (PI) with what is reported on the document. If the document matches the contents, you will sign the receipt and send it to the sponsor. If not, you will notify the sponsor.

Storage and safeguarding are the responsibility of the research center. The medication must be kept in a secure area with restricted access.

Storage temperature should be 2°C to 30°C.

The research center is required to record the temperature recorded in the *data logger* , using the designated format, every day while the protocol is in effect and has PIs. These data will be reviewed by the clinical monitor according to the *data logger records*.

In the event of material loss, this must be documented in the input and output log along with a clear description of the mechanism by which the loss occurred.

Upon completion of the protocol, all study materials will be retrieved by the sponsor as part of the closure audit. The final return of materials will be made by the principal investigator or the person designated by the principal investigator to return materials at the end of the study.

The sponsor reserves the right to initiate civil and criminal action against the principal investigator in the event of undocumented material missing at the end of the study.

## 6.3 Concomitant treatments and medications not authorized during the study

Subjects successfully enrolled in the study and who meet the eligibility criteria may continue systemic treatment for their underlying conditions. If they require the introduction of a new approved medication during the course of the study, they may do so. All concomitant medications used must be duly reported in the clinical record notes and in the corresponding section.

### Permitted medications:

- Ophthalmic:

All permitted medications administered ophthalmically during the study must wait a minimum of 10 minutes after the last application of the study or reference treatments. This is to avoid treatment interactions with the tear film, based on the tear flow rate and physiological tear volume. [30]

- Tetracaine 0.5%
- Tropicamide 0.8% / Phenylephrine 5%

- All topical antibiotics except tetracyclines
- Administered by a route other than ophthalmic:
  - Any medication whose effect may be susceptible to modifying any of the efficacy, safety or tolerability parameters of this research protocol must be notified to the clinical monitor or the sponsor's scientific committee to determine the appropriateness of the participant's admission, continuation or elimination as appropriate.
  - Women who enter using hormonal contraceptives must continue using them throughout the study.

Prohibited medications:

- Any medication with ophthalmic application that is not on the list of permitted medications
- Systemic steroids
- Immunomodulators
- Tetracyclines

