## 2.2 Background on the product under study

### 2.2.1 Pharmacology of the investigational product

Propylene glycol is considered a demulcent or humectant in ophthalmic lubricant formulations. These agents are used to lubricate the ocular surface, thereby helping to reduce associated discomfort and irritation.

Propylene glycol is a colorless, viscous, water-soluble polymer. Its chemical name is propane-1,2-diol (molecular formula:  $C_3H_8O_2$ ), with a molecular weight of 76.1 g/mol. [17, 18]

The physical properties of propylene glycol in contact with the ocular surface modify tear viscosity. The lipid layer of the nanoemulsion acts as a surfactant, helping to spread nonpolar lipids into the aqueous component of the tear film. It thus provides a barrier between the two phases and provides a support structure for the nonpolar phase. The combination of these helps reduce tear film evaporation.[19]

Due to the nature of propylene glycol, a large molecule that does not penetrate the ocular barrier, the pharmacokinetic profile of propylene glycol for ophthalmic administration has not been described. However, considering the route of elimination through the nasolacrimal duct, this fraction could follow the profile described for oral administration.

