### 7.4.2 Secondary outcome variables

- Changes in BCVA (TE: day 8 and 29)
- Changes in TRPL with fluorescein (TE: day 8 and 29)
- Corneal fluorescein staining changes (TE: day 8 and 29)
- Conjunctival staining changes with lissamine green (TE: day 8 and 29)
- Incidence of expected AEs (TE day 8 and 29)

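### The time from the last study drop to the break-up time and staining readings at V1 and VF is not standardised and need not be entered in the case report form, so change in break-up time can partly reflect a recent drop

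*Protocol*

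**What the plan says.** **Dosing.** Protocol 6.1.3: "The minimum dosage to follow is 1 drop, four times a day, in both eyes". It then allows that "subjects may increase the number of applications, if they deem necessary, as many times per day as they deem necessary". No clock times are given and visit days are not excepted.

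**Mechanism.** Protocol 2.2.1: "The physical properties of propylene glycol in contact with the ocular surface modify tear viscosity". The same section attributes reduced tear evaporation to the formulation.

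**Interval rule.** Under Protocol 6.3, permitted ophthalmic medications "must wait a minimum of 10 minutes after the last application of the study or reference treatments". The stated reason is to prevent interaction with the tear film. The rule governs other eye drops, not measurements.

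**Visits.** Protocol 7.5.1.2 and 7.5.1.3 list the tests in a suggested order (BCVA, TRPL, stains) without reference to the last study drop. Protocol 5.3 does set a condition before visits: "Avoid direct exposure to fans (including air conditioning vents) during activities that involve vision. 24 hours before your checkup visits". It has no counterpart for the last instillation.

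**Recording.** Each application goes in the Subject Diary (6.1.3, 7.4.4.7). The application figure that 7.4.4.7 sends to the FERC is the daily average. The SAP's variable table (6.0) and methods (7.0) contain no time-since-drop variable.

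**Analysis.** TRPL, staining and BCVA changes are secondary efficacy variables. Protocol 10.1.2 and SAP 7.0 plan within-group Wilcoxon tests for quantitative variables and McNemar tests for qualitative ones, as well as comparisons between groups.

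**The concern.** A lubricant that works by being on the eye may lengthen break-up time while it is there. At baseline no study drop has been given. At V1 and VF one subject may have instilled shortly before the test and another may have instilled last the previous night, and both follow the protocol. Change from baseline then combines the state of the tear film after a period of treatment with the short-lived presence of the latest drop, in unknown proportion.

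The within-arm tests are the most exposed, because randomisation does not protect a comparison with baseline. Baseline timing is loose as well: the eligibility criteria state no lubricant washout, so a subject's own product used just before VB could shift the change in the opposite direction. Between arms, uneven timing mostly adds variability. It becomes bias only if one arm instils more often or closer to the visit. The protocol keeps that possibility open by making daily applications an exploratory outcome to compare (3.3, 7.4.3).

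**Working it through.** The plan states no figure for this interval, so there is none to reproduce.

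**1. What each reading is timed from**

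| Reading | Timing given | Interval from last study drop |
|---|---|---|
| BCVA (7.4.4.3) | none | none stated |
| TRPL (7.4.4.4) | from the last blink, after fluorescein | indirect floor of about 10 min, no maximum |
| Corneal stain (7.4.4.5) | 4 to 8 min after the dye | same floor, no maximum |
| Conjunctival stain (7.4.4.6) | 1 to 4 min after the dye | same floor, no maximum |

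**2. Where the floor comes from.** Tetracaine is on the 6.3 list covered by the 10-minute wait. Protocol 5.2.1 names it among the compounds used in the tests. Section 7.4.4.5 has an anaesthetic drop before fluorescein, TRPL uses that fluorescein, and lissamine green follows. If 6.3 is obeyed, all three readings come at least about 10 minutes after the last study drop. BCVA needs no anaesthetic and is read earlier, so the rule does not reach it.

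**3. How widely the interval can vary (illustration).** Assumptions: a 16-hour waking day, evenly spaced drops and a visit at a random time. With k applications a day, gap = 960/k minutes, P(drop within 60 min) = 60/gap and P(drop within 10 min) = 10/gap.

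| k | Gap (min) | Within 60 min | Within 10 min |
|---|---|---|---|
| 4 | 240 | 25% | 4% |
| 6 | 160 | 37.5% | 6% |
| 8 | 120 | 50% | 8% |
| 12 | 80 | 75% | 12.5% |

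The interval can run from about 10 minutes to several hours, and it shortens as use rises.

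**4. What this could do to TRPL (assumed effect).** Suppose a drop within the past 60 minutes lengthens TRPL by D = 1 to 4 s. This is an assumption; the documents give no value.

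- Within an arm, contribution = D × P. At 4 a day: 1 × 0.25 = 0.25 s to 4 × 0.25 = 1.0 s. At 8 a day: 1 × 0.50 = 0.5 s to 4 × 0.50 = 2.0 s.
- Between arms, contribution = D × (difference in P). With equal use it is 0 in expectation. With 6 against 4 a day, the difference is 0.375 − 0.25 = 0.125, giving 1 × 0.125 = 0.125 s to 4 × 0.125 = 0.5 s.
- Use needed for a larger imbalance, starting from 25% at 4 a day: a 10-point gap needs k = 0.35 × 960/60 = 5.6 a day, and a 30-point gap needs k = 0.55 × 960/60 = 8.8 a day.

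These figures show how the problem scales. They are not estimates for this trial.

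**The case against.** The other side has a good deal to say.

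- **The readings are not simply uncontrolled.** The floor in step 2 is real. The suggested order also puts vital signs, medication review and refraction before TRPL, and at VF the OSDI and pregnancy test too. A waiting-room drop will usually be older than 10 minutes by then. This stands, but it limits only the short end of the interval.
- **The times may exist.** A reader might infer that instillation times go unrecorded. The documents do not show that: every instillation goes in the diary, whose form is not in the documents. What they do show is that no passage requires a clock time or its transfer to the FERC.
- **Presence on the eye may be the effect of interest.** Protocol 2.1 calls lubricants palliative, and 6.1.3.1 makes as-needed increases deliberate. Longer residence or more frequent use can fairly be called product effects. Even so, a reader of the results needs to know how soon after a drop the reading was taken.
- **Randomisation.** Both arms have the same regimen and masked packaging, so a common shift cancels in expectation. A reader might infer that the between-arm comparison is biased. The documents support that only conditionally, if use or timing differs by arm.
- **Acuity and staining.** A reader might extend the point equally to these. The documents expect blurring to last no more than 30 seconds (7.4.4.2) or one minute (2.4.1). Corneal staining counts epithelial erosions, and no mechanism is given by which a recent drop would change that count.

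**Conclusion.** The point holds as a limited, inexpensive improvement. The protocol neither standardises the interval from the last study drop to the TRPL and staining readings nor requires it in the FERC, and the SAP does not use it. For TRPL, the described mechanism and unlimited extra dosing make it plausible that part of the change from baseline reflects a recent drop. The consequence is mainly for the interpretation of within-arm tests and for variability; between-arm bias needs a difference in use or timing. The effect on staining is less certain, and a lasting effect on acuity has no support in the documents.

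No size can be derived from the documents: the seconds shown above rest on an assumed drop effect and an assumed pattern of use. A reader might also infer that the non-inferiority conclusion is at risk. It is not affected by this point, because the OSDI asks about the past week (Protocol 15.1) and is not a reading of the tear film at the visit.

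**What to change.** 1. In Protocol 7.5.1.2 and 7.5.1.3, have the site ask for the clock time of the last instillation and enter it in the FERC with the time of the TRPL and staining readings.
2. Have the sponsor state one common target interval for these readings and meet it by timing the reading at the visit, without asking subjects to withhold drops. Reconcile it with 6.1.3 and 6.3. Waiting helps only where the last drop was recent; longer intervals remain, which is why the time must be recorded.
3. At VB, record the time of last use of any prior lubricant.
4. In the SAP, summarise the interval by arm and visit. Add a sensitivity analysis of TRPL, with staining as supportive, that takes the interval into account in all subjects. Label it exploratory, because the interval arises after randomisation. Do not restrict the comparison to subjects who kept the interval, since that selects on behaviour after randomisation.

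Cost: a small timing entry in the FERC, and some readings taken later in the visit.

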#### 6.4 Procedure for monitoring and measuring adherence

For more than four decades, numerous studies have been conducted on the appropriate way to measure and quantify medication adherence, but none have reached a consensus that could serve as the gold standard, both in cross-sectional and longitudinal studies. [31, 32, 33, 34, 35, 36, 37, 38]

There are different procedures for measuring adherence to pharmacological interventions. The most common procedure involves self-reports, which include patient interviews, questionnaires, and self-monitoring diaries. Their strengths are speed, flexibility, low cost, and ease of implementation; they have a high degree of specificity for nonadherence, but their sensitivity and reliability for adherence are low. [38, 39]

Biochemical measurement of the drug, or its metabolite, is one of the methods that best confirms drug use. However, in addition to being costly and impractical, it is of little use in ophthalmic applications, as peripheral concentrations may be undetectable; and samples from other tissues require more invasive methods that would be inadvisable. [38]

Medication counting is another way to measure adherence. Classically referred to as "pill counting," in ophthalmology it is translated as the weight of the bottle. This is a simple, inexpensive, and noninvasive method. The main disadvantages of this method are: 1. It cannot confirm medication application (it could have been intentionally dropped or instilled outside the eye), and 2. It depends on the subject bringing the medication back. [38, 39]

A multi-method approach to adherence measurement is recommended. Because there is no ideal adherence measure, it is appropriate to use more than one method when aiming to achieve results that resemble reality. Selecting two or more methods allows for balancing their strengths and weaknesses, thus more accurately capturing adherence levels. [37]

Adhesion assessment will be based on the bottle's weight and will be performed taking into account the following information: drop weight, initial container weight, final container weight, and the total number of applications. The following simplified formula will be used:

$$Ad = \frac{(P_i - P_f)100}{P_T}$$

Where:

$Ad$  = adhesion

$P_i$  = weight of the container delivered to the subject at the beginning

$P_f$  = weight of the container returned by the subject

$P_T$  = weight of the dosage indicated for the investigational products

$$P_T = (P_g)G$$

Where:

$P_g$  = weight of a drop of the intervention, determined by the research and development department

$G$  = number of applications indicated for the investigational products

Packaging that does not maintain its physical integrity will not be considered for the calculation of adhesion.

In cases where the container is not returned, or has not maintained its physical integrity, adherence will be measured using the subject's diary, as follows:

$$Ad = (A_r)100/A_i$$

$Ad$  = Adhesion

$A_r$  = Registered applications

$A_i$  = Applications indicated for investigational products

The "indicated applications for investigational products" will correspond to a minimum dosage of 4 drops per day in each eye, i.e., 8 drops per day for 28 days (224). Because dosage increases are permitted, adherence rates greater than 100% may be observed.

The research center will designate a person responsible for monitoring adherence through a diary during visits. Measuring adherence through weight will be the sponsor's responsibility.

There is no standardized parameter for defining adequate adherence; it must be defined and outlined by the objectives of the particular research. [38]

For this study, a minimum adherence of 70% will be considered necessary to meet the research objectives. Therefore, subjects with less than 70% adherence will not be considered for the efficacy analysis; they will only be included in the safety analysis.

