#### *7.4.4.7 Number of applications made daily*

According to the PI dosing schedule, subjects may increase the number of daily instillations. They should not decrease the number to four per eye per day.

An instillation is considered separate when there are more than 10 minutes between each instillation. Similarly, if two or more drops are applied to a single eye during a single instillation, it will be considered one instillation. The subject must record each instillation performed during the day in the Subject Diary. The PI will tally the number of applications recorded in the diary and divide it by the number of days of treatment. This average will be recorded in the FERC.

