- Delivery of the PI and start of intervention: Refers to the delivery of the PI to the study patient by the research center. See
- EA Assessment: See 7.4.4.2
- Delivery of patient materials and instructions for completion: Refers to the IP providing the subject with the patient diary, identification card, and adherence-enhancing calendar. The assigned staff will provide the subject with pre-training on how to complete the diary.

#### 7.5.1.2 Visit 1

- Vital signs: See above
- Evaluation of concomitant medications: See above
- MAVC: Ver 7.4.4.3
- TRPL: See 7.4.4.4
- Ocular surface stains: See 7.4.4.5and 7.4.4.6
- Ophthalmological evaluation: See 7.4.4.2
- EA Assessment: See 7.4.4.2
- Subject Diary Assessment: This refers to the review of the Subject Diary instrument by the PI or designated facility staff; it will be reviewed for correct completion, as well as the patient's comments. The PI may question these comments for AEs. At the PI's discretion, the comments may or may not be reported as AEs.

- Adherence assessment: Adherence will be calculated by recording applications in the subject's diary. Adherence will be calculated based on a dosage of 4 applications per day. In addition, the average number of daily applications will be recorded according to section 7.4.4.7
- Subject Continuance Assessment: Refers to the PI's determination of the subject's desire to continue participating in the study.

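### The diary fallback for the 70% adherence rule has no defined unit and two conflicting denominators, so the same full use can score 50%, 100% or 200%

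*Protocol*

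**What the plan says.** **Dosing.** Protocol 6.1.3: "The minimum dosage to follow is 1 drop, four times a day, in both eyes". It also states that "subjects may increase the number of applications, if they deem necessary, as many times per day as they deem necessary", and each application is to be entered in the diary.

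**Main measure.** Protocol 6.4 takes the weight lost from the bottle, divided by the weight of one drop times the number of indicated applications. The latter is 4 drops a day in each eye, "8 drops per day for 28 days (224"). On totals above that it adds: "Because dosage increases are permitted, adherence rates greater than 100% may be observed".

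**Fallback.** If the bottle does not come back, or comes back damaged, 6.4 uses registered diary applications divided by the same indicated number. Protocol 10.1.3 and SAP 7.0 repeat the fallback without a denominator.

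**Other statements on the diary count.**
- Protocol 7.5.1.2 (Visit 1): "Adherence will be calculated based on a dosage of 4 applications per day". The final-visit section (7.5.1.3) only refers back for its adherence assessment.
- The variables table in 7.4.4 gives daily applications, counted from the diary, a reference value above 4.
- Protocol 7.4.4.7: "An instillation is considered separate when there are more than 10 minutes between each instillation". The same section counts repeat drops in a single eye at one sitting as one instillation, and refers to a number per eye per day.

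**Consequence.** Under 6.4 and 10.1.5, subjects below 70% are left out of the efficacy (per-protocol) set and kept for safety only.

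**The concern.** An adherence percentage means something only if numerator and denominator count the same thing. Here the denominator is 8 a day in one section and 4 a day in another, and the numerator is undefined. A subject who doses both eyes at one sitting might write one entry or two, and nothing in the documents settles which.

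The percentage decides membership of the set in which non-inferiority on the OSDI is tested. One mismatch excludes subjects who did everything asked of them. The opposite mismatch admits subjects who used far less than 70% of the indicated amount. Either way, who is analysed would depend on a counting convention chosen after the data exist.

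**Working it through.** **Inputs.** Minimum dosage of 1 drop, 4 times a day, in 2 eyes (6.1.3); 28 days, denominator 224 and the 70% cut (6.4); 4 applications a day for diary adherence (7.5.1.2).

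**Reproducing the plan's figure.** 4 × 2 × 28 = 224, as 6.4 states. On the 7.5.1.2 basis the denominator is 4 × 28 = 112.

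**Diary score for full use at the minimum dosage** (100 × registered / indicated):

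| A diary entry means | Registered | Over 224 (6.4) | Over 112 (7.5.1.2) |
|---|---|---|---|
| one both-eye occasion | 4 × 28 = 112 | 50% | 100% |
| one application in one eye | 8 × 28 = 224 | 100% | 200% |

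**What the 70% cut would then require.**
- Both-eye occasions over 224: 0.70 × 224 = 156.8 entries, and 156.8/28 = 5.6 occasions a day. That is 5.6/4 = 140% of the minimum dosage.
- Per-eye entries over 112: 0.70 × 112 = 78.4 entries, and 78.4/224 = 35% of the minimum dosage.
- Matched units: 70% in both cases, as intended.

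**Which unit do the documents point to?** The 4-a-day basis in 7.5.1.2 and the reference value above 4 in 7.4.4 suggest both-eye occasions. Section 6.4 suggests per-eye applications, because it multiplies the weight of one drop by the number of applications. Section 7.4.4.7 is worded partly per eye, but its merging rule concerns repeat drops in the same eye and does not say how dosing two eyes is entered.

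**Secondary check: the weight ratio over time.** The threshold is 156.8 drops. With both eyes dosed:
- 8 drops a day: 156.8/8 = 19.6, so day 20
- 12 drops a day: 156.8/12 = 13.1, so day 14
- 16 drops a day: 156.8/16 = 9.8, so day 10

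Drop volume and the number of bottles dispensed are not stated. Assuming 30 to 50 µL a drop, 156.8 drops take 4.7 to 7.8 mL, so even a single 10 mL bottle would not prevent this.

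**The case against.** The strongest defence is that 6.4 is consistent in itself. It treats an application as one drop in one eye, in the weight formula and in the figure of 224. If diary entries are read the same way, a fully compliant subject scores 224/224 = 100%. The 4-a-day basis in 7.5.1.2 belongs to monitoring at the visits, which 6.4 assigns to the centre, and no section says that figure decides the efficacy set. The diary form is not among the documents and may well have separate columns for each eye. The fallback is also needed only for bottles that are missing or damaged, and bottle return is scheduled at the final visit.

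Much of this stands. A reader might infer that the plan scores a compliant subject in the fallback at 50%. The documents do not support that: 50% follows only if an entry is a both-eye occasion and the denominator is 224. The defence does not supply the missing definition, though. The only description of how diary adherence is calculated at a visit uses 4 a day, and the fallback draws on that same diary.

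A reader might also infer from the cumulative weight ratio that bottle weight should give way, for every subject, to a diary measure capped at 100% a day. The documents do not support that either. Extra use is allowed on purpose (6.1.3), and totals above 100% are openly accepted. At exactly the minimum dosage, stopping before about day 20 is still caught. Section 6.4 itself calls the sensitivity and reliability of self-report for adherence low. Under 7.4.4.7 only the average daily count reaches the case report form, so a daily cap would mean transcribing up to 126 × 28 = 3,528 subject-days. That is a trade-off for the sponsor and not the correction of an error.

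**Conclusion.** The point holds as an undefined unit with conflicting denominators. The 8-a-day and 4-a-day bases stand in the text and need no assumption. The 50% and 200% scores are conditional: the first needs both-eye entries over 224, the second per-eye entries over 112, and the second would bear on the efficacy set only if the visit calculation were carried into the fallback. Both assume full use at the minimum dosage for 28 days.

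The reach is limited to subjects whose bottle is not returned or not intact. The documents give no proportion, and if every bottle comes back intact the effect on the efficacy set is nil. For a subject who does fall under it, the effect is decisive, because 50% and 100% lie on opposite sides of the cut.

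The cumulative ratio is a secondary note. A subject at 16 drops a day passes by day 10 and would remain in the efficacy set even if use then stopped, although the day-29 OSDI asks about the preceding week (Annex 15.1). How often this would happen cannot be judged from the documents.

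**What to change.** 1. Define the diary entry once, in Protocol 6.4, as either a both-eye occasion (denominator 4 × 28 = 112) or a per-eye application (denominator 8 × 28 = 224). Full use then scores 100%, and the same 70% cut applies.
2. Bring 7.4.4 (the reference value), 7.4.4.7, 7.5.1.2, 7.5.1.3 and SAP 7.0 into line with that definition, and check it against the layout of the diary form. If the form allows both ways of recording, add a conversion rule.
3. Reconcile the treatment length at the same time. SAP 3.1 gives 30 days and 6.4 gives 28. Thirty days at the minimum dosage is 240 drops, or 240/224 = 107% of the present denominator.
4. Keep bottle weight as the main measure. Use the diary as a supporting check for stopped days, for example by listing subjects who pass on weight but whose entries end early. This fits the reasoning in 6.4 that "Selecting two or more methods allows for balancing their strengths and weaknesses", and it need not alter the cut.

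Items 1 to 3 cost a few sentences and should be settled before the analysis, while group codes are still masked. Item 4 needs the date of the last entry taken from the diary, since the case report form holds only the average.
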